5.3.2.3.1. Estimator (Analysis) for the Supplementary Estimands of the Primary Endpoint

For testing of the primary endpoint using the supplementary estimands, the efficacy of each guselkumab group versus placebo will be compared, using the **Randomized Full Analysis Set** for Estimands 2 and 3, and the **Efficacy All Randomized and Treated Analysis Set** for Estimand 4. For all statistical comparisons, a Cochran-Mantel-Haenszel (CMH) test (2-sided) stratified by clinical remission status at maintenance baseline (Yes/No) and induction dose treatment will be used. Summaries of the proportion of participants in clinical remission at Week M-44 as well as the associated 95% confidence interval by treatment group, the adjusted treatment difference (with Cochran-Mantel-Haenszel weight) between each guselkumab treatment group and the placebo group, and the associated 95% confidence interval will be presented.

Missing data rule for Estimands 2-5:

After accounting for the ICE strategies, participants who are missing any or all of the Mayo subscores that comprise the primary endpoint at Week M-44 will be considered not to be in clinical remission at Week M-44 (i.e., nonresponder imputation).

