4. POPULATIONS (ANALYSIS SETS) FOR ANALYSIS

Analysis Sets	Description		
Participant Disposition Analysis Sets			
Enrolled Analysis Set	Includes all participants who are assigned to an intervention group in this		
	maintenance study, including both randomized and nonrandomized		
	participants.		
Full Analysis Set (FAS)	Includes all participants with a modified Mayo score of 5 to 9 who receive		
	at least 1 (partial or complete) dose of study intervention in this Maintenance		
	Study, including both randomized and nonrandomized.		
Randomized Analysis Set	Includes all participants who are randomized in the study (regardless of		
	modified Mayo score).		
Randomized (Modified Mayo 5-9)	Includes all participants who were randomized in the study with a modified		
Analysis Set	Mayo score of 5 to 9.		
Efficacy Analysis Sets: Participants in each efficacy analysis set will be analyzed according to their randomized or			
assigned study intervention regardless of the study intervention they actually received.			
Randomized Full Analysis Set	Includes all participants with a modified Mayo score of 5 to 9 who are		
	randomized (i.e., Guselkumab clinical responders at Week I-12 and Placebo		
	crossover responders at Week I-24 in an Induction Study) in this		
	Maintenance Study and receive at least 1 (partial or complete) dose of study		
	intervention in this maintenance study.		

CONFIDENTIAL – FOIA Exemptions Apply in U.S.

Statistical Analysis Flan CN1019390C03001 Amendment 2		
Analysis Sets	Description	
Nonrandomized Full Analysis Set	Includes all the participants with a modified Mayo score of 5 to 9 who enter this Maintenance Study but are not randomized (i.e., Guselkumab 24-week clinical responders, and Placebo responders at Week I-12 from Induction Study 1 or Induction Study 2) and receive at least 1 (partial or complete) dose of study intervention in this Maintenance Study.	
Efficacy All Randomized and Treated Analysis Set	Includes all participants (regardless of modified Mayo score) who are randomized (i.e., Guselkumab clinical responders at Week I-12 and Placebo crossover responders at Week I-24 in an Induction Study) in this Maintenance Study and receive at least 1 (partial or complete) dose of study intervention in this Maintenance Study.	

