5.3.2.3. Supplementary Estimands for the Primary Endpoint

Estimand 2 (Composite Strategy for all ICEs):

The attributes of this supplementary estimand are the same as those for the primary estimand with the exception of the Variable (Endpoint) and the strategies for the intercurrent events, which are described as follows:

Variable (Endpoint): Clinical remission at Week M-44, where participants are considered to have achieved clinical remission if they fulfill the clinical remission criteria based on modified Mayo score components (Section 5.3.1.). Participants who have intercurrent events in categories 1-6 prior to the Week M-44 visit will be considered to not have achieved clinical remission at Week M-44.

Intercurrent Events and corresponding strategies:

For this estimand, the intercurrent events (given below) are addressed with a Composite Strategy.

- 1. An ostomy or colectomy (partial or total)
- 2. Have a dose adjustment (including a sham dose adjustment; Section 1.3.1.)
- 3. Prohibited change in UC medication (described in Attachment 2)
- 4. Discontinuation of study intervention due to lack of efficacy or an AE of worsening of UC
- 5. Discontinuation of study intervention due to COVID-19 related reasons (excluding COVID-19 infection) or regional crisis in Russia and Ukraine
- 6. Discontinuation of study intervention due to reasons other than those in ICEs 4 and 5

Estimand 3 (Alternative Mayo Calculation 1):

The attributes of this supplementary estimand are the same as those for the primary estimand with the exception of the Variable (Endpoint), where clinical remission at Week M-44 based on modified Mayo score components will be derived using an alternative calculation for the Mayo rectal bleeding subscore and stool frequency subscore instead of the methodology based on 3-day diary as detailed in Section 5.3.1. In this estimand, the Mayo rectal bleeding and stool frequency subscores will be calculated either based on eligible diary data (data not excluded from the calculation per Section 5.3.1.1.) collected on 3 consecutive days or, when 3 consecutive days are not available, all eligible diary data collected in a 7-day window prior to a clinical visit. If neither 3 consecutive days nor 4 nonconsecutive days are available, then the Mayo rectal bleeding and stool frequency subscores will not be calculated.

Estimand 4 (Alternative Mayo Calculation 2):

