The attributes of this supplementary estimand are the same as those for the primary estimand with the exception of the Variable (Endpoint), where clinical remission at Week M-44 based on modified Mayo score components will be derived using an alternative calculation for the Mayo rectal bleeding subscore and stool frequency subscore instead of the methodology based on 3-day

diary as detailed in Section 5.3.1. In this estimand, the Mayo rectal bleeding and stool frequency subscores will be calculated based on all available diary data collected in the 7-day window prior to a clinical visit, excluding the day of an endoscopy and the day prior to an endoscopy. If neither 3 consecutive days nor 4 non-consecutive days are available, then the Mayo rectal bleeding and stool frequency subscores will not be calculated.

Estimand 5 (Different Population):

The attributes of this supplementary estimand are the same as those for the primary estimand with the exception of Population as defined below, which will include all participants randomized under the inclusion/exclusion criteria:

Population: Patients 18 years or older with moderately to severely active UC as reflected in the inclusion/exclusion criteria (Protocol Section 5), which includes patients with a modified Mayo score of 4 to 9.

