5.4.1.3. Main Estimators (Analyses) for the Secondary Estimands

The major secondary endpoint analyses will be based on the **Randomized Full Analysis Set**. For all statistical comparisons of the major secondary endpoints (except for clinical remission at Week M-44 among the participants who had achieved clinical remission at maintenance baseline), a CMH test (2-sided) stratified by clinical remission status at maintenance baseline (Yes/No) and induction dose treatment (guselkumab 400 mg, guselkumab 200 mg, placebo crossover to guselkumab 200 mg) will be used. In cases of rare events, Fisher's exact test will be used for treatment comparisons.

For clinical remission at Week M-44 among the participants who had achieved clinical remission at maintenance baseline, a CMH test (2-sided) stratified by induction dose treatment (guselkumab 400 mg, guselkumab 200 mg, placebo crossover to guselkumab 200 mg) will be used.

Summaries of the proportion of participants achieving each major secondary endpoint by treatment group as well as the associated 95% confidence interval, the adjusted treatment difference (with Cochran-Mantel-Haenszel weight) between each guselkumab treatment group and the placebo group, as well as the associated 95% confidence interval will be presented.

Missing Data Rules for the Secondary Estimands:

After accounting for the ICE strategies, any missing data for the major secondary endpoints will be handled with nonresponder imputation. In particular, the following rules will be used:

[figure not shown]
- Participants who are missing any or all of the 3 Mayo subscores that comprise the modified Mayo score will be considered not to have achieved corticosteroid-free clinical remission, maintenance of clinical response, or maintenance of clinical remission.
- Participants who have a missing endoscopy subscore at Week M-44 will be considered not to have achieved endoscopic healing or histologic-endoscopic mucosal healing or endoscopic normalization at Week M-44.
- Participants who are missing any or all of the components in the Geboes grading system pertaining to histologic healing endpoint will be considered not to have achieved histologic-endoscopic mucosal healing.
- Participants who are missing either stool frequency or rectal bleeding subscores at Week M-44 will be considered not to have achieved symptomatic remission at Week M-44.

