5.4.2. Supplementary Estimands for the Major Secondary Endpoints

Estimand 6 (Composite Strategy for all ICEs):

The attributes and strategies for the ICEs that were used for the Supplementary Estimand 2 for the primary endpoint (Section 5.3.2.2.2.) in which all ICEs are handled by the composite strategy, will also be used for each of the major secondary endpoints.

Estimand 7 (Alternative Mayo Calculation 1):

This estimand applies to symptomatic remission at Week M-44, corticosteroid-free clinical remission at Week M-44, clinical response at Week M-44 (maintenance of clinical response at M-44), and clinical remission at Week M-44 among the participants who had achieved clinical remission at maintenance baseline (maintenance of clinical remission at Week M-44).

The attributes of this supplementary estimand are the same as those for the main estimand with the exception of the Variable (Endpoint), where symptomatic remission, clinical response, and clinical remission criteria will be derived using an alternative calculation for the Mayo rectal bleeding subscore and stool frequency subscore instead of the methodology based on 3-day diary as detailed in Section 5.3.1.1. In this estimand, the Mayo rectal bleeding and stool frequency subscores will

be calculated either based on eligible diary data collected on 3 consecutive days or, when 3 consecutive days are not available, all eligible diary data collected in a 7-day window prior to a clinical visit. If neither 3 consecutive days nor 4 nonconsecutive days are available, then the Mayo rectal bleeding and stool frequency subscores will not be calculated.

Estimand 8 (Alternative Mayo Calculation 2):

This estimand applies to symptomatic remission at Week M-44, corticosteroid-free clinical remission at Week M-44, clinical response at Week M-44 (maintenance of clinical response at Week M-44), and clinical remission at Week M-44 among the participants who had achieved clinical remission at maintenance baseline (maintenance of clinical remission at M-44).

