5.4.2.1. Estimator (Analyses) for the Supplementary Estimands

The same analysis methods for the main estimands described in Section 5.4.1.3. will be used for the supplementary estimands of the major secondary endpoints, using the **Randomized Full Analysis Set** for Estimands 5 and 6, and the **Efficacy All Randomized and Treated Analysis Set** for Estimand 7.

Missing Data Rules for the Supplementary Estimands

The same missing data rules for the main estimands described in Section 5.4.1.3. will be used for the supplementary estimands of the major secondary endpoints.

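### The SAP's analysis-set rules use estimand numbers that no longer match the definitions: Estimands 4 and 7 get the wrong set, and Estimands 5 and 9 are not given the set they need

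*SAP*

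**What the plan says.** SAP Section 5.3.2.3 defines four supplementary estimands for the primary endpoint, and Section 5.4.2 defines four more for the major secondary endpoints.

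- Estimands 2 and 6 apply the composite strategy to all intercurrent events.
- Estimands 3 and 7 use the first alternative diary calculation, and Estimands 4 and 8 the second. Section 5.3.2.3 labels the fourth "Estimand 4 (Alternative Mayo Calculation 2)". All four differ from the primary or main estimand only in the Variable attribute.
- Estimands 5 and 9 differ only in the Population attribute, "which includes patients with a modified Mayo score of 4 to 9".

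The sets are assigned elsewhere. Section 5.3.2.3.1 uses the Randomized Full Analysis Set (RFAS) "for Estimands 2 and 3, and the Efficacy All Randomized and Treated Analysis Set for Estimand 4". The heading of its missing-data rule is "Missing data rule for Estimands 2-5". Section 5.4.2.1 carries over the analysis methods of Section 5.4.1.3 and uses the RFAS "for Estimands 5 and 6, and the Efficacy All Randomized and Treated Analysis Set for Estimand 7". Section 5.4.1.3 itself states: "The major secondary endpoint analyses will be based on the Randomized Full Analysis Set".

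Section 4 restricts the RFAS to modified Mayo 5 to 9. Its entry for the Efficacy All Randomized and Treated Analysis Set begins "Includes all participants (regardless of modified Mayo score) who are randomized".

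**The concern.** The set rules and the estimand definitions do not agree. A supplementary estimand is informative when it changes one attribute and holds the others fixed. Estimand 4 was added at a Health Authority's request to show what happens when the bleeding and stool subscores use all available diary days apart from the endoscopy day and the day before it. Run on the set named for it, it also brings in participants whom the primary estimand excludes. Any departure from the primary result would then mix two causes. The same applies to Estimand 7.

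For Estimands 5 and 9 the problem is reversed. They exist to add the modified Mayo 4 participants, yet neither is given the set that contains them. Whoever programs these analyses must decide which part of the SAP to disregard.

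A smaller related error is that the definition of Estimand 6 refers to "Supplementary Estimand 2 for the primary endpoint (Section 5.3.2.2.2"), but that section is the multiple-imputation sensitivity analysis. Estimand 2 is defined in Section 5.3.2.3.

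**Working it through.** **Definitions against assigned sets.** The primary estimand (Section 5.3.2) requires modified Mayo 5 to 9. An estimand that changes only the Variable or the intercurrent-event strategies keeps that population and needs the RFAS. One that widens the population to 4 to 9 needs the Efficacy All Randomized and Treated Analysis Set (ART below).

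| Estimand | What changes | Set implied | Set in the text | Result |
|---|---|---|---|---|
| 2 | Intercurrent-event strategy | RFAS | RFAS | agrees |
| 3 | Diary calculation 1 | RFAS | RFAS | agrees |
| 4 | Diary calculation 2 | RFAS | ART | contradicts |
| 5 | Population 4 to 9 | ART | none in 5.3.2.3.1 | gap |
| 6 | Intercurrent-event strategy | RFAS | RFAS | agrees |
| 7 | Diary calculation 1 | RFAS | ART | contradicts |
| 8 | Diary calculation 2 | RFAS | unnamed; RFAS via 5.4.1.3 | agrees by default |
| 9 | Population 4 to 9 | ART | unnamed; RFAS via 5.4.1.3 | contradicts by default |

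The number 5 does appear in Section 5.4.2.1, against the RFAS. That section covers only the major secondary endpoints, so it does not govern Estimand 5, and if it did, the RFAS would conflict with the 4-to-9 population. The missing-data rule in 5.3.2.3.1 runs through Estimand 5, which confirms that Estimand 5 belongs to that section.

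**Pattern.** Reading the numbers in the two set rules as 4→5, 5→6, 6→7 and 7→9 makes every named assignment correct. Only Estimands 4 and 8 are then left without a set, and these are the two that the Amendment 2 summary of changes lists as added. This points to numbers not updated after the insertion. It is an inference, since the preceding SAP text is not available, and the contradiction does not depend on it.

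**Size of the set difference.** The plan's projection reproduces: 596 × 0.60 = 357.6 and 354 × 0.60 × 0.60 = 127.4. Rounded down, these give 357 + 127 = 484, as in SAP Table 2. Score-4 enrolment is capped at 5% of the total programme population. Their share of the randomized maintenance participants is not given, so a range of 0 to 5% is assumed.

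With share *s* of all randomized and treated participants, the number added to an RFAS of *n* is *n* × *s* / (1 − *s*):

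- *n* = 484: *s* = 1% gives 4.9; 2.5% gives 12.4; 5% gives 25.5 (about 8 per group)
- *n* = 404, *s* = 5%: 21.3
- *n* = 525, *s* = 5%: 27.6

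**Possible shift in the treatment difference.** If the treatment difference among score-4 participants departs from that in the rest by *g* points, the overall difference moves by *s* × *g*. The documents give no value for *g*, so 10 to 30 points is assumed for illustration.

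- *s* = 5%: 0.05 × 10 = 0.5 points, up to 0.05 × 30 = 1.5 points
- *s* = 1%: 0.1 to 0.3 points

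For comparison, the planned difference is 45% − 25% = 20 points. With 161 per group its standard error is √(0.25 × 0.75/161 + 0.45 × 0.55/161) = 0.052, or 5.2 points.

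**The case against.** The best case for leaving this alone is that the intent can be recovered. Estimands 5 and 9 are labelled as population changes, their population is written out, and only one randomized efficacy set in Section 4 admits score 4. On this reading the defect is a numbering slip, the numerical effect is well inside the standard error, no confirmatory result depends on it, and Section 5.5 already plans a separate descriptive summary of the score-4 participants. It can also be said that the default for Estimands 8 and 9 is inferred: Section 5.4.2.1 carries over methods and then names sets separately. Finally, the programme-wide 5% cap does not strictly bound the share among induction responders who are rerandomized.

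Part of this stands. The effect is small, the cap-based count is illustrative, and the default for Estimand 9 comes from reading two sections together. But Section 5.4.1.3 ties the major secondary analyses to the RFAS, and no other rule is available for Estimand 9. For Estimands 4 and 7, recovering the intent means overriding an explicit instruction, which a pre-specified plan should not require. The descriptive summary uses the standard score calculation and assigns no set to any estimand, so it does not separate the two changes. The mistaken cross-reference for Estimand 6 is unlikely to mislead, because the same sentence describes the strategy correctly.

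**Conclusion.** The concern holds. Of the eight supplementary estimands, two have a set that contradicts their definition (4 and 7), one has no set in its own section (5), one is unnamed with a conflicting default (9), and four are right (2, 3 and 6 by name, 8 by default).

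The consequence is interpretive more than numerical: 0 to about 25 participants on 484, and at most about 1.5 points on the treatment difference. Both figures rest on the assumed 0 to 5% share, and the second also on the assumed gap of 10 to 30 points. Only supplementary analyses are affected. It should be fixed because the rule as written yields the wrong analysis for an estimand that a Health Authority requested.

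**What to change.** - **Section 5.3.2.3.1:** assign the Randomized Full Analysis Set to Estimands 2, 3 and 4, and the Efficacy All Randomized and Treated Analysis Set to Estimand 5.
- **Section 5.4.2.1:** assign the Randomized Full Analysis Set to Estimands 6, 7 and 8, and the Efficacy All Randomized and Treated Analysis Set to Estimand 9.
- **Section 5.4.2, Estimand 6:** change the cross-reference from 5.3.2.2.2 to 5.3.2.3.

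The cost is two sentences and one reference, to be corrected before the Week M-44 database lock. No new data or analyses are needed.

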5.4. Major Secondary Endpoints Analysis

5.4.1. Confirmatory Major Secondary Endpoints

The following are the major secondary endpoints, presented in the order in which they will be tested for the global testing procedure (Section 5.4.1.3.):

- 1. Symptomatic remission at Week M-44.
- 2. Endoscopic healing at Week M-44.
- 3. Corticosteroid-free (i.e., not requiring any treatment with corticosteroids for at least 8 weeks prior) clinical remission at Week M-44.
- 4. Clinical response at Week M-44 (maintenance of clinical response at M-44).

- Statistical Analysis Plan CNTO1959UCO3001 Amendment 2
- 5. Histologic-endoscopic mucosal healing at Week M-44.
- 6. IBDQ remission at Week M-44.
- 7. Fatigue response at Week M-44.
- 8. Clinical remission at Week M-44 (maintenance of clinical remission at M-44) among the participants who had achieved clinical remission at maintenance baseline.
- 9. Endoscopic normalization at Week M-44.

5.4.1.1. Definition of Endpoints

The following endpoints are defined based on the corresponding scales; certain ICEs will be incorporated in the variable definition of each estimand as appropriate:

Clinical response: A decrease from induction baseline in the modified Mayo score (Section 5.3.1.1) by $\ge 30\%$ and ≥ 2 points, with either a ≥ 1 -point decrease from baseline in the rectal bleeding subscore or a rectal bleeding subscore of 0 or 1.

Symptomatic remission: a stool frequency subscore of 0 or 1 and a rectal bleeding subscore of 0, where the stool frequency subscore has not increased from induction baseline.

Histologic healing: neutrophil infiltration in < 5% of crypts, no crypt destruction, and no erosions, ulcerations or granulation tissue according to the Geboes grading system³ (i.e., Geboes score ≤ 3.1). (See Attachment 3).

Endoscopic healing: an endoscopy subscore of 0 or 1 with no friability present on the endoscopy.

Endoscopic normalization: An endoscopy subscore of 0 (which requires that no friability is present).

Histologic-endoscopic mucosal healing: achieving a combination of histologic healing and endoscopic healing with no friability present on the endoscopy.

IBDQ remission: total IBDQ score ≥ 170 (Irvine et al, 1994¹³; Higgins et al, 2005¹⁴).

Fatigue response: $a \ge 7$ -point improvement from induction baseline in PROMIS-Fatigue short form 7a.

Corticosteroid-free Clinical remission: not requiring any treatment with corticosteroids for at least 8 weeks prior to Week M-44 and also meeting the criteria for clinical remission at Week M-44.

5.4.1.2. Main Estimands for the Major Secondary Endpoints

The attributes and strategies for the ICEs that were used for the primary estimand (Estimand 1) for the primary endpoint analysis (Section 5.3.2.) will also be used for each of the major secondary endpoints.

5.4.1.3. Main Estimators (Analyses) for the Secondary Estimands

The major secondary endpoint analyses will be based on the **Randomized Full Analysis Set**. For all statistical comparisons of the major secondary endpoints (except for clinical remission at Week M-44 among the participants who had achieved clinical remission at maintenance baseline), a CMH test (2-sided) stratified by clinical remission status at maintenance baseline (Yes/No) and induction dose treatment (guselkumab 400 mg, guselkumab 200 mg, placebo crossover to guselkumab 200 mg) will be used. In cases of rare events, Fisher's exact test will be used for treatment comparisons.

For clinical remission at Week M-44 among the participants who had achieved clinical remission at maintenance baseline, a CMH test (2-sided) stratified by induction dose treatment (guselkumab 400 mg, guselkumab 200 mg, placebo crossover to guselkumab 200 mg) will be used.

Summaries of the proportion of participants achieving each major secondary endpoint by treatment group as well as the associated 95% confidence interval, the adjusted treatment difference (with Cochran-Mantel-Haenszel weight) between each guselkumab treatment group and the placebo group, as well as the associated 95% confidence interval will be presented.

Missing Data Rules for the Secondary Estimands:

After accounting for the ICE strategies, any missing data for the major secondary endpoints will be handled with nonresponder imputation. In particular, the following rules will be used:

[figure not shown]
- Participants who are missing any or all of the 3 Mayo subscores that comprise the modified Mayo score will be considered not to have achieved corticosteroid-free clinical remission, maintenance of clinical response, or maintenance of clinical remission.
- Participants who have a missing endoscopy subscore at Week M-44 will be considered not to have achieved endoscopic healing or histologic-endoscopic mucosal healing or endoscopic normalization at Week M-44.
- Participants who are missing any or all of the components in the Geboes grading system pertaining to histologic healing endpoint will be considered not to have achieved histologic-endoscopic mucosal healing.
- Participants who are missing either stool frequency or rectal bleeding subscores at Week M-44 will be considered not to have achieved symptomatic remission at Week M-44.
- Participants who have a missing IBDQ total score at Week M-44 will be considered not to have achieved IBDQ remission at Week M-44.
- Participants who have any missing PROMIS-Fatigue short form 7a item at Week M-44 will be considered not to have achieved fatigue response at Week M-44.

Testing Procedure:

The United States and the global regions will employ a different multiple testing strategy as described below to control the overall Type I error.

[figure not shown]
Type I error control in countries outside the United States (global testing procedure): A hierarchical testing procedure as shown in Figure 4a will be employed to control the overall Type 1 error rate over the 9 major secondary efficacy analyses at the (2-sided) 0.05 significance level within a guselkumab dose group, for the doses that test positive for the primary endpoint. A major secondary endpoint for a guselkumab dose group will be considered significant only if all the previous endpoints in the hierarchy and the current endpoint test positive at the 2-sided 0.05 level of significance. If an endpoint is not significant, all subsequent tests in the hierarchy will be considered not to be significant.

Figure 4a: Global Testing Procedure for the Primary and Major Secondary Endpoints at Week M-44

Type I error control in the United States (US-specific testing procedure): A hierarchical testing procedure as shown in Figure 4b will be employed for the United States to strongly control the overall Type 1 error rate at the 0.05 level across the primary and all major secondary endpoints and across the 2 guselkumab doses. An endpoint will be considered significant only if all the previous endpoints in the hierarchy and the current endpoint test positive at the 2-sided 0.05 level of significance. If an endpoint is not significant, all subsequent tests in the hierarchy will be considered not to be significant. Note that the rank order of the major secondary endpoints is different for the US-specific and global testing procedures due to regional preferences. In addition, the major secondary endpoint of IBDQ remission at Week M-44 will not be included in the US-specific testing procedure since the FDA does not accept the IBDQ endpoint to support future labeling claims due to consideration that the IBDQ is not a validated instrument.

Figure 4b: US Specific Testing Procedure for the Primary and Major Secondary Endpoints at Week M-44

